Immune mediated: Adverse events (both serious and non-serious) associated with nivolumab may represent immunologic etiology. Nivolumab must be held for suspected immune-mediated toxicities or severe/life-threatening AEs of particular interest (in Section 7.0) and immune-related toxicities (in Appendix D). Please review both Sections (7 and Appendix D) prior to infusion of nivolumab in any patient in whom immune-mediated toxicity is suspected.

If the investigator is unsure if a particular toxicity at least possibly represents an immune mediated toxicity to nivolumab, the treating physician should follow section 7 and appendix D and treat as immune mediated, until it is confirmed as not being immune mediated. Consultation with BrUOG is suggested in such situations. BrUOG will share information about the situation with the BrUOG Reviewer and PI and provide the site guidance, as available.

Removal from study (all cohorts):

Patients must discontinue nivolumab permanently for the following:

- Any Grade 2 drug-related uveitis or eye pain or blurred vision that does not respond to topical therapy and does not improve to Grade 1 severity within the re-treatment period OR requires systemic treatment
- Grade 3 drug-related thrombocytopenia > 7 days or associated with bleeding
- Any treatment delay resulting in no nivolumab dosing for > 6 weeks.
- Patients who discontinue nivolumab during definitive chemoradiation (cohorts one and three)
- Grade 4 drug-related endocrinopathy adverse events such as adrenal insufficiency, ACTH deficiency, hyper- or hypothyroidism, or glucose intolerance, hypophysitis.
- \geq Grade 4 hepatic AEs
- \geq Grade 4 skin toxicity (per Appendix D can delay or discontinue for grade 3. Must come off, as per this bullet for grade 4 skin)
- ALL OTHER treatment related grade 3/4 treatment related events with the following exceptions:
 - Grade 4 neutropenia \leq 7 days;
 - Grade 4 lymphopenia or leukopenia;
 - isolated Grade 4 electrolyte imbalances/abnormalities that are not associated with clinical sequelae and are corrected with supplementation/appropriate management within 72 hours of their onset;
 - Grade 3 hepatic AEs that return to Grade 2 or less within 5 days Of note, this overrides Appendix D
 - Skin toxicity \leq grade 3 that improves with steroid therapy. NOTE: Any rash consistent with Stevens-Johnson Syndrome or Toxic Epidermal Necrolysis requires permanent discontinuation of nivolumab.
 - Grade 3 renal toxicity (as per Appendix D)

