If Nivolumab is discontinued, the patient is to be taken off study. The total treatment patient BrUOG 355: 7/8/17, 7/11/17, 7/20/17, 8/7/17, 8/8/17, 8/14/17, 8/16/17, 8/21/17, 8/22/17, 8/24/17, 8/28/17, 9/5/17, 9/6/17, 9/8/17, 9/11/17, 11/7/17, 11/8/17, 11/19/17 approved DD, 11/20/17, 12/12/17, 12/14/17, 1/29/18, 2/1/18, 2/6/18, 2/7/18, 2/8/18, 2/9/18, 2/12/18, 2/13/18, 3/8/18 all reviews, 3/9/18, 3/13/18, 3/14/18, 3/15/18, 4/19/18, 4/23/18, 5/29/18, 6/5/18, Amendment # 1 7/9/18, Amendment # 2 12/12/18, Amendment #3, 4/6/2020, Amendment #4 5/11/2020

received will be collected, but once patient is off study, all treatment is per standard of care and does not need to follow-BrUOG 355.

In situations when RT is not given (held for toxicity or other reasons (weather, machine is down, holiday), cisplatin and Nivolumab should not be given and should also be held.

If Nivolumab is held on a day Cisplatin is due and the patient meets criteria to receive Cisplatin and Radiation then every attempt should be made to administer Cisplatin and radiation, while holding Nivolumab.

Every attempt should be made for all patients to complete radiation therapy (even if cisplatin and nivolumab are held)

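### As written, the catch-all removal rule in 5.5.1 ends nivolumab for grade 3 cytopenias and corrected electrolyte events but spares the qualifying grade 4 forms

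*Combined protocol and SAP*

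**What the plan says.** The removal list in section 5.5.1 applies to all cohorts and opens with a mandatory lead-in: "Patients must discontinue nivolumab permanently for the following". After several specific bullets it ends with a catch-all, "ALL OTHER treatment related grade 3/4 treatment related events with the following exceptions", followed by six exceptions.

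- Three exceptions name grade 4 alone. They are neutropenia of at most 7 days, "Grade 4 lymphopenia or leukopenia", and "isolated Grade 4 electrolyte imbalances/abnormalities that are not associated with clinical sequelae", the last with the further condition of correction within 72 hours of onset.
- Three exceptions name grade 3: hepatic events that recover to grade 2 or less within 5 days, skin toxicity (a less-than-or-equal sign followed by "grade 3 that improves with steroid therapy"), and renal toxicity.

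The consequence goes beyond the drug: "If Nivolumab is discontinued, the patient is to be taken off study". Later treatment is then standard of care and need not follow the protocol.

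**The concern.** A stopping rule should not treat a lower grade more harshly than a higher grade of the same event. Here grade 3 lymphopenia, leukopenia, neutropenia and promptly corrected isolated electrolyte abnormalities fall under the catch-all and match none of the exceptions, while the qualifying grade 4 forms are let through.

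A site that follows the text ends nivolumab for the milder event. A site that infers the intent holds the drug and resumes it. Exposure to nivolumab, and removal from study, would then depend on who reads the bullet. Section 1.2 makes the feasibility of adding nivolumab a primary objective, so inconsistent or needless loss of the drug matters.

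**Working it through.** The plan states no figure to reproduce. The check applies the rule to each event type and then counts the doses at stake.

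**Step 1. Apply the rule.** An event triggers removal under this bullet if it is treatment-related, is grade 3 or 4, is not covered by an earlier bullet, and matches no exception. The only earlier bullet on blood counts is "Grade 3 drug-related thrombocytopenia > 7 days or associated with bleeding", which does not reach the events below.

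| Treatment-related event | Grade 3 | Grade 4 |
|---|---|---|
| Lymphopenia | remove | spared |
| Leukopenia | remove | spared |
| Neutropenia, 7 days or less | remove | spared |
| Neutropenia, over 7 days | remove | remove |
| Isolated electrolyte event, no sequelae, corrected within 72 h | remove | spared |

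The order of severity is inverted for all four event types, for neutropenia only when it is short. This concerns the one bullet. A grade 4 patient can still be removed by another route, for example "Any treatment delay resulting in no nivolumab dosing for > 6 weeks".

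**Step 2. Compare with the rest of the protocol.**

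- The hold rule in 5.5.1 lets nivolumab resume once haematological or other toxicity with some causality to it has recovered to grade 2 or less, or baseline. That implies some grade 3 events are survivable on study, but it states no exception to the removal list.
- Grade 3 thrombocytopenia removes a patient only if prolonged or with bleeding. Grade 3 lymphopenia of any duration would remove one.
- Section 6.1 requires an ANC of at least 1000/mcL for cisplatin, and 5.5.1 skips nivolumab when cisplatin is held. A low count there costs a dose, not the drug.
- Section 6.2 restarts radiation after grade 4 neutropenia improves, even with nivolumab on hold. Footnote e of the section 11 calendar ends extra blood counts at grade 3 or less.

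All four suggest that grade 4 was meant as the highest grade tolerated. However, the same list uses inequality signs when it means a range (at most grade 3 for skin, at least grade 4 for hepatic and skin), so a bare grade 4 can fairly be read as exactly grade 4.

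**Step 3. Reach.** Section 5.5.1 does not define treatment-related.

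- *Broad reading:* section 8.7 lists nivolumab, cisplatin and radiation as study treatment. The bullet then covers expected events. Section 5.6 links low magnesium and potassium to cisplatin, and 7.1.3 describes electrolyte losses as common and usually correctable.
- *Narrow reading (nivolumab only):* the nivolumab events listed in 8.1 include none of the four types, so the rule may bite rarely.

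**Step 4. Doses lost per removed patient.** Inputs from 5.3 and 5.4: two induction doses; three concurrent doses in cohorts 1 and 3, every 14 days from day 1 of radiation (days 1, 15, 29); maintenance every 4 weeks for 2 years in cohorts 2 and 3.

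- Maintenance doses: 104 weeks / 4 = about 26.
- Planned totals: cohort 1, 2 + 3 = 5; cohort 2, 2 + 26 = 28; cohort 3, 2 + 3 + 26 = 31.

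| Event during chemoradiation | Cohort 1 | Cohort 3 |
|---|---|---|
| After day 1 dose | 5 − 3 = 2 (40%) | 31 − 3 = 28 (90%) |
| After day 15 dose | 5 − 4 = 1 (20%) | 31 − 4 = 27 (87%) |
| After day 29 dose | 5 − 5 = 0 | 31 − 5 = 26 (84%) |

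Cohort 2 has no concurrent doses: 28 − 2 = 26 lost (93%). Patients due maintenance, from 16.2: 4 + up to 12 = up to 16 of 24.

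**The case against.** The strongest reply accepts the wording and disputes its importance.

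- **The intent is clear.** A clinician who sees grade 4 lymphopenia exempted would ordinarily treat grade 3 as exempt. Section 16.1.1 also sets aside uncomplicated neutropenia and clinically insignificant laboratory changes when judging safety. This is persuasive about intent, but reaching it means overriding a mandatory instruction. The consultation with the coordinating group suggested in 5.5.1 concerns doubt about immune mediation, so it does not settle this question.
- **The narrow reading fits better.** The heading of 5.5.1 sends readers to section 6 for cisplatin and radiation rules, and 7.1.2 handles grade 3–4 nausea and vomiting by skipping a nivolumab dose, not ending the drug. That weighs against the broad reading. Against it, neighbouring bullets say drug-related where this one says treatment related, so the point remains open. On the broad reading, those sections conflict further with the removal list.
- **The dose losses are maxima.** They assume every remaining dose would otherwise be given, with no progression or other reason to stop. In cohort 2, which has chemoradiation alone at that stage, the figure also needs either the broad reading or attribution back to the induction doses. Both caveats stand.
- **Trial decisions are untouched.** This also stands: the thresholds in 16.1.1 do not count discontinuations, and under 7.3 patients removed for toxicity are still followed unless they withdraw consent.

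**Conclusion.** The concern holds. On its wording, the catch-all bullet removes patients for grade 3 lymphopenia, leukopenia, neutropenia and promptly corrected isolated electrolyte events while sparing the qualifying grade 4 forms, and no other section exempts grade 3. It affects three of six exceptions and four event types.

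The frequency cannot be derived: the documents give no event rates, and the scope of treatment-related is unsettled. The doses counted above are upper limits per removed patient, for events during chemoradiation and, in cohorts 1 and 3, after the day 1 concurrent dose. The harm is needless or inconsistent loss of nivolumab, not a wrong cohort decision. Because the rule is mandatory and the correction is nearly free, it should be fixed.

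**What to change.** Amend three exceptions in 5.5.1:

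1. Lymphopenia or leukopenia: grade 3 or 4.
2. Isolated electrolyte abnormalities: grade 3 or 4, keeping both conditions (no clinical sequelae, corrected within 72 hours of onset).
3. Neutropenia: at minimum, grade 3 or 4 lasting 7 days or less. The sponsor should decide whether grade 3 needs a duration limit at all.

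Keep the existing hold until grade 2 or less, or baseline, so that nobody is dosed with unresolved grade 3 toxicity attributed to nivolumab. The same amendment could usefully state whether treatment-related means nivolumab alone or all three treatments, since that governs how often the bullet applies.

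The cost of the three edits is wording in an amendment and one sponsor decision on the neutropenia limit. No extra data, visits or patients are needed.

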5.6 Definitive Chemoradiation Plan

Standard therapy guidelines for definitive chemoradiation in cervical cancer will be utilized during this trial. All patients will receive tailored pelvic (if para-aortic nodes are negative) and/or extended field, pelvis+para-aortic, radiation therapy (if para-aortic nodes are involved) with a plan for daily delivery of RT (Monday-Friday) for approximately 6 weeks (which may include brachytherapy).

Cisplatin:

40 mg/m² of cisplatin (maximum total dose of 70 mg/week and maximum BSA=1.75m²)

Dosing on Days: 1, 8, 15, 22, 29, 36 (preferably on Mondays or Tuesdays). The only exception allowed is to account for holidays or unexpected events that warrant closure of the radiation oncology or infusion center, in which case treatment is allowed within the next fully operational day. For example, if D8 falls on a holiday, treatment with cisplatin (and with nivolumab if scheduled) should occur on next day, which will be counted as D8 with all subsequent days rescheduled to allow for a 7-day interval between dosing.

- Cisplatin should be infused **over approximately 1 hour**, beginning on day 1 of radiation therapy.

One hour before cisplatin administration, 500-1000 ml of normal saline should be infused intravenously, as per institutional standard of care.

Appropriate antiemetics should be administered prior to cisplatin. Additional fluid may be given as needed for symptomatic support. Premedications for nausea and vomiting prophylaxis should follow institutional guidelines.

Immediately after completion of the cisplatin infusion, an additional 500-1000 ml normal saline should be infused over one hour. It is highly recommended that KCl 20-40 meq and MgSO₄ 2 grams be added to the normal saline in the post hydration fluid given that hypomagnesemia and

BrUOG 355: 7/8/17, 7/11/17, 7/20/17, 8/7/17, 8/8/17, 8/14/17, 8/16/17, 8/21/17, 8/22/17, 8/24/17, 8/28/17, 9/5/17, 9/6/17, 9/8/17, 9/11/17, 11/7/17, 11/8/17, 11/19/17 approved DD, 11/20/17, 12/12/17, 12/14/17, 1/29/18, 2/1/18, 2/6/18, 2/7/18, 2/8/18, 2/9/18, 2/12/18, 2/13/18, 3/8/18 all reviews, 3/9/18, 3/13/18, 3/14/18, 3/15/18, 4/19/18, 4/23/18, 5/29/18, 6/5/18, Amendment # 1 7/9/18, Amendment # 2 12/12/18, Amendment #3, 4/6/2020, Amendment #4 5/11/2020

hypokalemia are associated with cisplatin therapy. **This is the minimum fluid administration recommendation and more fluid may be given at the discretion of the treating physician and institutional standard of care should be followed.**

On days when Cisplatin and Nivolumab are administered the same day, Nivolumab is to be administered first, followed by the normal saline flush of the line.

After Nivolumab administration, administer one hour of normal saline (500-1000 ml), 1 hour of Cisplatin, then 1 hour of normal saline (500-1000 ml). It is highly recommended KCl 20-40 meq and MgSO₄ 2 grams added. Radiation would then commence post completion of Cisplatin and normal saline.

5.7 Radiation specifications

This protocol requires photon external beam radiation therapy (EBRT), either 3D conventional radiation therapy (3D- CRT) or intensity modulated radiation therapy (IMRT) techniques followed by low dose rate (LDR) or high dose rate (HDR) brachytherapy. Radiation therapy must be completed within 60 days of initiation. Four-field box 3D-CRT and IMRT are pretreatment stratification variables.

- For 3D-CRT, the prescription dose is 45 Gy in 25 fractions at 1.8 Gy/fraction with an optional parametrial boost of 5.4 Gy in three fractions at 1.8 Gy/fraction. EBRT should be given once daily Monday-Friday, 5 fractions per week.
- For IMRT, the prescription dose is 45 Gy in 25 fractions at 1.8 Gy/fraction, unless a simultaneous integrated boost (SIB) is used for gross nodal disease. For SIB cases, the primary target will receive 47.6 Gy in 1.7 Gy/fraction and the gross nodal PTV (PTV_Boost) will receive 1.93-2.12 Gy per fraction, depending on bowel tolerance. IMRT should be given once daily Monday-Friday, 5 fractions per week.
- For brachytherapy, the prescription doses are 27.5 - 30 Gy for HDR.

Cohort 1A - Extended-Field Radiation Therapy (EFRT) - EFRT will be used for patients with any positive common iliac LN requiring extension of the superior border of the radiation field above the L4-L5 inter-space as detailed in Section 5.7.1.

Cohort 1B -Whole Pelvic Radiation Therapy (WPRT) - WPRT will be used for patients without evidence of high common iliac LN necessitating EFRT. The traditional whole pelvic radiation field borders are as detailed in Section 5.7.1.

5.7.1 Treatment technology

BrUOG 355: 7/8/17, 7/11/17, 7/20/17, 8/7/17, 8/8/17, 8/14/17, 8/16/17, 8/21/17, 8/22/17, 8/24/17, 8/28/17, 9/5/17, 9/6/17, 9/8/17, 9/11/17, 11/7/17, 11/8/17, 11/19/17 approved DD, 11/20/17, 12/12/17, 12/14/17, 1/29/18, 2/1/18, 2/6/18, 2/7/18,2/8/18, 2/9/18, 2/12/18, 2/13/18, 3/8/18 all reviews, 3/9/18, 3/13/18, 3/14/18, 3/15/18, 4/19/18, 4/23/18, 5/29/18, 6/5/18, Amendment # 1 7/9/18, Amendment # 2 12/12/18, Amendment #3, 4/6/2020, Amendment #4 5/11/2020

Conventional 3D RT (4-field box)

Conventional 3D plans will consist of a 4-field box arrangement using AP/PA and Right/Left lateral fields. Conventional RT must use 4-25 MV photons. It is permissible i) to use bone landmarks to draw field borders as described below or ii) to use 3D planning with explicit targets as outlined in section 5.2.3. Custom cerrobend blocks or MLCs are acceptable for field shaping.

If bone landmarks are used, use the following portals:

- Superior border: L4-L5 interspace. For patients with positive high common iliac LN, an extended field will be used such that the superior border will extend above L4-L5 interspace to cover additional para-aortic LN at least 3cm above the superior-most extent of gross nodal disease.
- Lateral border: 1-2 cm lateral to the border of the true pelvis
- Inferior border: Obturator foramen or 3 cm inferior to the lowest extent of disease, whichever is lower
- Anterior border: line from pubic symphysis to 1.5 cm anterior to common iliac nodes at L4-5. At least 0.5 cm anterior of the L4-L5 vertebral bodies should be included in the field in order to adequately encompass the low para-aortic region.
- Posterior border: draw border 1.0 cm posterior to the sacrum from S1-S4
- Custom blocking to shield femoral heads. Do not block the obturator foramen or within 1 cm of the common iliac nodes

Opposed lateral pelvic fields are used using the same isocenter as the anterior and posterior pelvic fields. The superior and inferior borders will be the same as for the anterior and posterior fields.

The inferior extent or vaginal extension of disease should be marked so that the inferior border of disease can be documented. Uninvolved normal tissues may be blocked although the position of the uterus should be contoured to ensure adequate coverage.

For patients who underwent lymph node dissection: If clips are present to document the position of the lymph nodes, these should be used as a guide when anterior blocks are designed to shield small bowel. When shielding bowel, at least 3 cm should not be blocked anterior to the L4 and L5 vertebral bodies in order to adequately encompass the low para-aortic region.

IMRT

IMRT plans may include static field arrangements (e.g. 5-9 fields), modulated arc therapy, or Tomotherapy. Pseudo-step-wedge intensity modulation (PSWIM) or volumetric modulated arc therapy (VMAT) techniques are permitted. IMRT should use 6-15 MV photons.

Parametrial boost

After conventional RT or IMRT delivery, a parametrial boost can be delivered at the treating

BrUOG 355: 7/8/17, 7/11/17, 7/20/17, 8/7/17, 8/8/17, 8/14/17, 8/16/17, 8/21/17, 8/22/17, 8/24/17, 8/28/17, 9/5/17, 9/6/17, 9/8/17, 9/11/17, 11/7/17, 11/8/17, 11/19/17 approved DD, 11/20/17, 12/12/17, 12/14/17, 1/29/18, 2/1/18, 2/6/18, 2/7/18, 2/8/18, 2/9/18, 2/12/18, 2/13/18, 3/8/18 all reviews, 3/9/18, 3/13/18, 3/14/18, 3/15/18, 4/19/18, 4/23/18, 5/29/18, 6/5/18, Amendment # 1 7/9/18, Amendment # 2 12/12/18, Amendment #3, 4/6/2020, Amendment #4 5/11/2020

physician's discretion. The parametrial boost will use an AP/PA field arrangement. The superior border should be reduced to include only the true pelvis and the upper border of the true pelvis is defined as 1 cm above the inferior aspect of the sacroiliac joint. The inferior border remains the same as in the pelvis fields. A parametrial central field block is a minimum of 4 cm wide.

Brachytherapy

Patients will be treated using HDR brachytherapy for all patients treated on this protocol. Tandem and ring or tandem and ovoids will be used for intact cervix brachytherapy. Interstitial brachytherapy such as with a Vienna applicator is allowed at the discretion of the treating physician. A tandem and cylinder or tandem alone is allowed only for patients where tandem and ring or ovoid application is not possible due to extent of disease or poor anatomy (e.g., obliterated fornices).

Use of IMRT or other external beam techniques in place of brachytherapy to boost gross cervical disease is discouraged. If deemed necessary or essential for the patient's care (e.g., if a patient refuses brachytherapy), reasons for not performing brachytherapy should be documented.

5.7.2 Immobilization and simulation

Conventional RT

CT simulation is required. Field outlines should be drawn electronically on Digitally Reconstructed Radiographs (DRRS) produced from the CT simulation information. Localization or block-check-images of simulated fields are to be obtained in a simulator and/or treatment machine. Digital pictures of all treatment portals with the patient in the treatment position are to be submitted for quality assurance review. All treatment fields, whether formed by cerrobend blocks or multi-leaf collimation, should be independently checked against the corresponding DRRs. Prone positioning with bowel exclusion devices (e.g. belly boards) is allowed.

3D planning is at the physician's discretion. If 3D planning is being done, a CT simulation scan is required with a slice thickness ≤ 3.0 mm for the regions extending at least 4cm above and below target volumes. Patients can be simulated supine or prone. All subjects will have a customized immobilization device (e.g., Alpha Cradle or Vac-Loc) fabricated at the time of simulation. A full bladder is required at the time of simulation and treatment. Intravenous contrast is recommended to visualize vessels better. Oral or rectal contrast is not recommended for treatment planning.

IMRT

All subjects will undergo a CT (or PET/CT) simulation scan in the supine position using a slice thickness ≤ 3.0 mm and large field-of-view pelvic protocol. A customized immobilization device fabricated at the time of simulation is required. It is recommended that CT scans be obtained from the T12 vertebral body to 5 cm below the ischial tuberosities. For patients undergoing CBCT with each fraction, it is recommended that the isocenter be placed along the patient's midline 1.5 cm caudal to the inferior border of the sacroiliac joint. Otherwise, isocenter

BrUOG 355: 7/8/17, 7/11/17, 7/20/17, 8/7/17, 8/8/17, 8/14/17, 8/16/17, 8/21/17, 8/22/17, 8/24/17, 8/28/17, 9/5/17, 9/6/17, 9/8/17, 9/11/17, 11/7/17, 11/8/17, 11/19/17 approved DD, 11/20/17, 12/12/17, 12/14/17, 1/29/18, 2/1/18, 2/6/18, 2/7/18, 2/8/18, 2/9/18, 2/12/18, 2/13/18, 3/8/18 all reviews, 3/9/18, 3/13/18, 3/14/18, 3/15/18, 4/19/18, 4/23/18, 5/29/18, 6/5/18, Amendment # 1 7/9/18, Amendment # 2 12/12/18, Amendment #3, 4/6/2020, Amendment #4 5/11/2020

placement is left to the discretion of the treating physician. It is recommended to use a consistent bladder filling state (e.g. always full or always empty) for simulation and treatment. It is recommended for patients not to be simulated or treated with a full rectum as this may result in poor setup reproducibility. Bowel preparatory agents (enema, stool softeners, etc.) may be applied at the discretion of the physician. Oral contrast is optional. Radio-opaque cervical markers or implanted fiducials are optional

The volume irradiated will include the totality of the gross disease locally and regionally, as visualized by CT scan, the whole uterus, paracervical, parametrial and uterosacral ligaments as well as the areas of the obturator, hypogastric, external and internal iliac lymph nodes. In patients treated with extended fields the para-aortic regions with a minimum margin of 2 cm should be included. A margin of 2-3 cm should be given around the gross disease and 1.5-2 cm around uninvolved lymph nodes.

Brachytherapy

For 3D brachytherapy planning, all subjects will undergo a CT (or PET/CT) simulation scan using a slice thickness ≤ 3.0 mm with brachytherapy applicators and dummy sources in. It is recommended that CT scans contain the entire brachytherapy applicators and the critical structures such as bladder and rectum.

Maintaining applicator position is required from the time of applicator insertion to simulation and treatment. Before a CT scan, a Foley catheter is inserted into the bladder and the balloon must be filled with 7 cc of radio-opaque fluid to define the bladder reference point in treatment planning.

For volume-directed brachytherapy, pelvic MRI (≤ 3 mm slice thickness) is required with either the first or second insertion. An MRI-compatible applicator is required to perform volume-directed brachytherapy. Subsequent insertions may use CT or MRI for planning.

